5.4.2 Safety Measures

All the AEs, SAEs and other safety reporting will be captured as per GSK standard procedures.

- Solicited local symptoms during the 7-day post-vaccination follow-up
- Solicited general symptoms during the 7-day post-vaccination follow-up
- Unsolicited symptoms during the 21-day post-vaccination follow-up period
- SAEs during the 21-day post-vaccination follow-up period

5.4.3 Physical Examinations

A physical examination of each participant will be performed before vaccination. The collected information will be recorded in the medical history section of the eCRF. Treatment of any abnormality observed during the physical examination will be performed outside this trial according to local medical practice guidelines or by referral to an appropriate health care provider.

5.4.4 Vital Signs

Vital signs (blood pressure, pulse rate, respiratory rate, and body temperature) will be assessed pre-vaccination at Day 1.

5.4.5 Electrocardiograms

Not applicable.

5.4.6 Clinical Safety Laboratory Assessments

Not applicable.

CONFIDENTIAL

Phase IV Clinical Trial Protocol

GlaxoSmithKline
A phase IV trial of *Fluarix Tetra* in Indian
adults aged 65 years and older
Version 2.0, dated: 05 May 2023
Protocol/ Study No.: 218702
Page 39 of 74

5.4.7 Suicidal Risk Monitoring

Not applicable.

5.5 Adverse Events

Definition of AE: An AE is any untoward medical occurrence (an unfavorable/unintended sign - including an abnormal laboratory finding), symptom, or disease (new or exacerbated) in a trial participant that is temporally associated with the administration of a marketed vaccine. The AE may or may not be considered related to the marketed vaccine.

Events Meeting the AE Definition:

- Significant or unexpected worsening or exacerbation of the condition/indication under trial.
- Exacerbation of a chronic or intermittent pre-existing condition including either an increase in frequency and/or intensity of the condition.
- New conditions detected or diagnosed following the performance of the administration of marketed vaccine even though they may have been present before trial start.
- Signs, symptoms, or the clinical sequelae of a suspected drug, disease, or other interaction.
- Signs, symptoms, or the clinical sequelae of administration error of either the marketed vaccine or a concurrent medication.
- Signs or symptoms temporally associated with the marketed vaccine.
- Signs, symptoms that require medical attention (e.g., hospital stays, physician visits and emergency room visits).
- Significant failure of an expected pharmacologic or biological action.
- Clinically significant abnormal laboratory findings or other abnormal assessments that are present at baseline and significantly worsen following the start of the trial will also be reported as AEs or SAEs.
- The signs, symptoms, and/or clinical sequelae resulting from lack of efficacy will be reported as AE or SAE if they fulfill the definition of an AE or SAE.

Events NOT Meeting the AE Definition

- Situations where an untoward medical occurrence did not occur (e.g., social and/or convenience admission to a hospital, admission for routine examination).
- Anticipated day-to-day fluctuations of pre-existing disease(s) or condition(s) present or detected at the start of the trial that do not worsen.

CONFIDENTIAL

- Pre-existing conditions or signs and/or symptoms present in a participant before the administration of the trial vaccine. These events will be recorded in the medical history section of the eCRF.
- Hospitalization for elective treatment of a pre-existing condition (known or diagnosed before signing the informed consent) that did not worsen from baseline.
- Any clinically significant abnormal laboratory findings or other abnormal safety assessments associated with the underlying disease, unless judged by the Investigator to be more severe than expected for the participant's condition.

Definition of SAE: A SAE is any untoward medical occurrence that:

- a. Results in death.
- b. Is life-threatening.
- c. Requires hospitalization or prolongation of existing hospitalization.
- d. Results in disability/incapacity.
- e. Is a congenital anomaly/birth defect in the offspring of a trial participant.

Other adverse events (AEs): Other AEs not included in the list of solicited AEs that are experienced by the participants within 21 days post-vaccination (i.e., the day of vaccination and the following 6 days) will be collected in the free-text field of the diary card. Other AEs include both serious and non-serious AEs.

Participants will be instructed to contact the Investigator immediately should they/the participant manifest any signs or symptoms perceived as serious/of concern or indicating a change in their health status.

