5.5.2 Method of Detecting AEs and SAEs

A diary card will be used in this trial to capture solicited and other AEs. In addition to the participant completing and returning the diary card, the Investigator will record any occurrence of SAEs into the participant's eCRF to minimize potential missing data (e.g., when a participant's hospitalization prevents the completion of the diary). An AE that is assessed as severe should not be confused with a SAE. Severity is a categorization used for rating the intensity of an event; and both AEs and SAEs can be assessed as severe. An event is defined as 'serious' when it meets 1 of the pre-defined outcomes as described above ([Section 5.5](#)).

Assessment of Intensity

The intensity of the following solicited AEs will be assessed as described:

Table 3. Intensity Scales for Solicited Events in Adults 18 years of Age or More

Event	Intensity Grade	Parameter
Pain at administration-site	0	None
	1	Mild: Any pain neither interfering with nor preventing normal everyday activities
	2	Moderate: Painful when limb is moved and interferes with everyday activities
	3	Severe: Significant pain at rest. Prevents normal everyday activities
Headache	0	Normal
	1	Mild: Headache that is easily tolerated

CONFIDENTIAL
Phase IV Clinical Trial Protocol

GlaxoSmithKline
 A phase IV trial of *Fluarix Tetra* in Indian
 adults aged 65 years and older
 Version 2.0, dated: 05 May 2023
 Protocol/ Study No.: 218702
 Page 42 of 74

Event	Intensity Grade	Parameter
	2	Moderate: Headache that interferes with normal activity
	3	Severe: Headache that prevents normal activity
Fatigue	0	Normal
	1	Mild: Fatigue that is easily tolerated
	2	Moderate: Fatigue that interferes with normal activity
	3	Severe: Fatigue that prevents normal activity
Muscle ache all over body	0	Normal
	1	Mild: Muscle aches that are easily tolerated
	2	Moderate: Muscle aches that interfere with normal activity
	3	Severe: Muscle aches that prevent normal activity
Joint pain	0	Normal
	1	Mild: Joint pain that is easily tolerated
	2	Moderate: Joint pain that interferes with normal activity
	3	Severe: Joint pain that prevents normal activity
Shivering (chills)	0	Normal
	1	Mild: Shivering (chills) that is easily tolerated
	2	Moderate: Shivering (chills) that interferes with normal activity
	3	Severe: Shivering (chills) that prevents normal activity
Sweating	0	Normal
	1	Mild: Sweating that is easily tolerated
	2	Moderate: Sweating that interferes with normal activity

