	3	Severe: Sweating that prevents normal activity
Gastrointestinal symptoms: nausea, vomiting, diarrhea and/or abdominal pain	0	Normal
	1	Mild: Gastrointestinal symptoms that are easily tolerated
	2	Moderate: Gastrointestinal symptoms that interfere with normal activity
	3	Severe: Gastrointestinal symptoms that prevent normal activity
Redness at administration-site		Record greatest surface diameter in mm
Swelling at administration-site		Record greatest surface diameter in mm
Temperature*		Record temperature in °C/°F

* Fever is defined as temperature $\geq 38.0^{\circ}\text{C}$ (100.4°F) by any route. The preferred location for measuring temperature will be the oral route.

The maximum intensity of local injection site redness/swelling will be scored at GSK as follows:

0: ≤ 20 mm
 1: > 20 to 50 mm

CONFIDENTIAL

Phase IV Clinical Trial Protocol

GlaxoSmithKline
A phase IV trial of *Fluarix Tetra* in Indian
adults aged 65 years and older
Version 2.0, dated: 05 May 2023
Protocol/ Study No.: 218702
Page 43 of 74

2: >50 to 100 mm
3: >100 mm

The maximum intensity of fever will be scored at GSK as follows:

0:	<38.0°C (<100.4°F)
1:	≥38.0–38.4°C (≥100.4–101.2°F)
2:	≥38.5–38.9°C (≥101.3–102.1°F)
3:	≥39.0–40.0°C (≥102.2–104.0°F)
4:	>40.0°C (>104.0°F)

The Investigator will assess the maximum intensity that occurred over the duration of the event for all unsolicited AEs (including SAEs) recorded during the study. The assessment will be based on the Investigator's clinical judgment.

The intensity should be assigned to one of the following categories:

1 (mild)	= An AE which is easily tolerated by the participant, causing minimal discomfort, and not interfering with everyday activities.
2 (moderate)	= An AE which is sufficiently discomforting to interfere with normal everyday activities.
3 (severe)	= An AE which prevents normal, everyday activities In adults, such an AE would, for example, prevent attendance at work/school and would necessitate the administration of corrective therapy.

An AE that is assessed as Grade 3 (severe) should not be confused with an SAE. Grade 3 is a category used for rating the intensity of an event; and both AEs and SAEs can be assessed as Grade 3. An event is defined as 'serious' when it meets 1 of the pre-defined outcomes as described in the [Section 5.5](#).

CONFIDENTIAL

Phase IV Clinical Trial Protocol

GlaxoSmithKline
A phase IV trial of *Fluarix Tetra* in Indian
adults aged 65 years and older
Version 2.0, dated: 05 May 2023

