Protocol/ Study No.: 218702
Page 44 of 74

Assessment of causality

All solicited administration-site and systemic events will be considered causally related to vaccination. The complete list of these events is provided in the [Table 5](#).

The Investigator must assess the relationship between study vaccine/product and the occurrence of each unsolicited AE/SAE using clinical judgment. Where several different vaccines/products were administered, the Investigator should specify, when possible, if the unsolicited AE/SAE could be causally related to a specific vaccine/product (i.e., investigational, control/placebo or co-administered vaccine). When causal relationship to a specific vaccine/product cannot be determined, the Investigator should indicate the unsolicited AE/SAE to be related to all products.

Alternative plausible causes, such as natural history of the underlying diseases, concomitant therapy, other risk factors, and the temporal relationship of the event to the study vaccine/product will be considered and investigated. The investigator will also consult the investigator brochure (IB) to determine his/her assessment.

Causality should be assessed by the Investigator using the following question:

Is there a reasonable possibility that the unsolicited AE may have been caused by the study vaccine/product?

YES	:	There is a reasonable possibility that the study vaccine/product contributed to the AE.
NO	:	There is no reasonable possibility that the AE is causally related to the administration of the study vaccine/product. There are other, more likely causes and administration of the study vaccine/product is not suspected to have contributed to the AE.

If an event meets the criteria to be determined as ‘serious’ (see [Section 5.5](#)), additional examinations/tests will be performed by the Investigator to determine ALL possible contributing factors for each SAE.

Possible contributing factors include:

- Medical history.
- Other medication.

CONFIDENTIAL

Phase IV Clinical Trial Protocol

GlaxoSmithKline
A phase IV trial of *Fluarix Tetra* in Indian
adults aged 65 years and older
Version 2.0, dated: 05 May 2023
Protocol/ Study No.: 218702
Page 45 of 74

- Protocol required procedure.
- Other procedure not required by the protocol.
- Lack of efficacy of the vaccine/product, if applicable.
- Erroneous administration.

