8. SAFETY REPORTING

The Investigator or site staff is/are responsible for the detection, documentation and reporting of events meeting the criteria and definition of an AE or SAE as provided in this protocol.

Each participant will be instructed to contact the Investigator immediately should he/she experience any signs or symptoms he/she perceives as serious.

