8.1 Definitions

Adverse events (AEs)

An AE is any untoward medical occurrence in a clinical investigation participant, temporally associated with the use of a medicinal product, whether or not considered related to the medicinal product.

A SAE is any untoward medical occurrence that:
a. Results in death.
b. Is life-threatening.

CONFIDENTIAL

Phase IV Clinical Trial Protocol

GlaxoSmithKline
A phase IV trial of *Fluarix Tetra* in Indian
adults aged 65 years and older
Version 2.0, dated: 05 May 2023
Protocol/ Study No.: 218702
Page 63 of 74

Note: The term 'life-threatening' in the definition of 'serious' refers to an event in which the participant was at risk of death at the time of the event. It does not refer to an event, which hypothetically might have caused death, had it been more severe.

c. Requires hospitalization or prolongation of existing hospitalization

Note: In general, hospitalization signifies that the participant has been admitted at the hospital or emergency ward for observation and/or treatment that would not have been appropriate in the physician's office or in an outpatient setting. Complications that occur during hospitalization are also considered as AEs. If a complication prolongs hospitalization or fulfills any other serious criteria, the event will also be considered serious. When in doubt as to whether 'hospitalization' occurred, or was necessary, the AE should be considered serious.

d. Results in disability/incapacity

Note: The term disability means a substantial disruption of a person's ability to conduct normal life functions. This definition is not intended to include experiences of relatively minor medical significance such as uncomplicated headache, nausea, vomiting, diarrhea, influenza like illness, and accidental trauma (e.g. sprained ankle) which may interfere or prevent everyday life functions but do not constitute a substantial disruption.

e. Is a congenital anomaly/birth defect in the offspring of a trial participant.**f. Abnormal pregnancy outcomes (e.g. spontaneous abortion, fetal death, stillbirth, congenital anomalies, ectopic pregnancy).****g. Other situations**

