Medical or scientific judgment should be exercised in deciding whether reporting is appropriate in other situations, such as important medical events that may not be immediately life-threatening or result in death or hospitalization but may jeopardize the participant or may require medical or surgical intervention to prevent one of the other outcomes listed in the above definition. These should also be considered serious. Examples of such events are invasive or malignant cancers, intensive treatment in an emergency room or at home for allergic bronchospasm, blood dyscrasias or convulsions that do not result in hospitalization.

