4.4.1.3. Serious Adverse Event

An SAE is any untoward medical occurrence that:
a. Results in death
b. Is life-threatening

Note: The term 'life-threatening' in the definition of 'serious' refers to an event in which the participant was at risk of death at the time of the event. It does not refer to an event, which hypothetically might have caused death, had it been more severe.

c. Requires hospitalization or prolongation of existing hospitalization

Note: In general, hospitalization signifies that the participant has been admitted at the hospital or emergency ward for observation and/or treatment that would not have been appropriate in the physician's office or in an outpatient setting. Complications that occur during hospitalization are also considered as AEs. If a complication prolongs hospitalization or fulfills any other serious criteria, the event will also be considered serious. When in doubt as to whether 'hospitalization' occurred, or was necessary, the AE should be considered serious.

d. Results in disability/incapacity

Note: The term 'life-threatening' in the definition of 'serious' refers to an event in which the participant was at risk of death at the time of the event. It does not refer to an event, which hypothetically might have caused death, had it been more severe.

e. Is a congenital anomaly/birth defect in the offspring of a trial participant
f. Abnormal pregnancy outcomes (e.g. spontaneous abortion, fetal death, stillbirth, congenital anomalies, ectopic pregnancy)
g. Other situations

Medical or scientific judgment should be exercised in deciding whether reporting is appropriate in other situations, such as important medical events that may not be immediately life-threatening or result in death or hospitalization but may jeopardize the participant or may require medical or surgical intervention to prevent one of the other outcomes listed in the above definition. These should also be considered serious. Examples of such events are invasive or malignant cancers, intensive treatment in an emergency room or at home for allergic bronchospasm, blood dyscrasias or convulsions that do not result in hospitalization.

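### The SAE list in Protocol 5.5, which 5.5.2 cites for seriousness, omits the important-medical-event criterion in Protocol 8.1 and SAP 4.4.1.3; 5.5 also miscounts its 21-day window

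*Protocol*

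**What the plan says.** Protocol 5.5 introduces its SAE criteria with "Definition of SAE: A SAE is any untoward medical occurrence that" and lists five: death, threat to life, hospitalization, disability or incapacity, and congenital anomaly. It has no catch-all item and no reference to 8.1.

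Section 5.5.2 relies on that list three times:

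- In the detection text: "An event is defined as 'serious' when it meets 1 of the pre-defined outcomes as described above", with a link to 5.5.
- After the intensity scales: "An event is defined as 'serious' when it meets 1 of the pre-defined outcomes as described in the", again followed by a link to 5.5.
- Under causality, where meeting the 5.5 criteria means that "additional examinations/tests will be performed by the Investigator to determine ALL possible contributing factors for each SAE".

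Protocol 8.1 gives seven criteria. Item f covers abnormal pregnancy outcomes. Item g covers other situations, including important medical events, and says of them "These should also be considered serious". SAP 4.4.1.3 has the same seven; its item g begins "Medical or scientific judgment should be exercised in deciding whether reporting is appropriate in other situations, such as important medical events".

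Section 8 opens by making sites responsible for "events meeting the criteria and definition of an AE or SAE as provided in this protocol", without naming 5.5 or 8.1.

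On the time window, the paragraph on other AEs in 5.5 gives 21 days after vaccination and then explains it in brackets as vaccination day plus six further days.

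**The concern.** An event that meets only item g is serious under Protocol 8.1 and the SAP but not under the list that 5.5.2 cites. One of the examples in 8.1 is allergic bronchospasm managed intensively at home or in an emergency department. That is relevant here because the Rationale names allergic reaction as a risk of influenza vaccines. Item f is immaterial at age 65 and over, and Protocol 5.5.5 marks pregnancy as not applicable.

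If a site classed such an event as non-serious by following 5.5.2 to 5.5, three things would follow:

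- It would leave the 21-day SAE primary endpoint.
- It would not trigger the contributing-factor work-up in 5.5.2.
- It would not fall under the follow-up to resolution that 5.5.3 sets for SAEs.

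If it were also judged unrelated, and 8.1 were not applied, it could miss the 24-hour reporting in 5.5.1 and 8.3. A related event would still be reported, because 8.3 also covers related non-serious AEs.

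The SAP would not recover the classification. Section 6.2.3 analyses data as recorded in the eCRF, and the SAP states no step for reassessing seriousness against its own list.

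**Working it through.** **The lists side by side**

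| Criterion | Protocol 5.5 | Protocol 8.1 | SAP 4.4.1.3 |
|---|---|---|---|
| a to e | yes | yes | yes |
| f, pregnancy outcomes | no | yes | yes |
| g, other situations | no | yes | yes |
| Total | 5 | 7 | 7 |

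The difference that can matter is g. The Documentation of Protocol Amendments table suggests how it arose: detailed SAE definitions were added to 8.1, and no matching change is listed for the definition in 5.5. That is background only, since the conflict is in current text.

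**Reproducing the plan's own figures.** Protocol Table 8 takes N = 250 and an SAE incidence rising linearly to 1% at 6 months. The chance of at least one participant with an SAE is 1 − (1 − p)^250.

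- Month 1: p = 1%/6, giving 34.1%, as printed.
- Month 6: p = 1%, giving 91.9%, as printed. SAP Table 3 prints 91.1% here, a transcription mismatch with no bearing on this point.

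**SAEs of any kind in 21 days**

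- p = 1% × 21/(6 × 30.44) = 0.115%
- Expected participants = 250 × 0.00115 = 0.29
- Chance of at least one = 1 − (1 − 0.00115)^250 = 25.0%

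**SAEs meeting only g.** The documents give no share. I assume 5% to 30%.

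- At 5%: expected 250 × 0.00115 × 0.05 = 0.014; chance of any = 1 − (1 − 0.00115 × 0.05)^250 = 1.4%
- At 30%: expected 250 × 0.00115 × 0.30 = 0.086; chance of any = 1 − (1 − 0.00115 × 0.30)^250 = 8.3%

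These are chances that such an event occurs at all. The chance that one occurs and is then misclassified is lower, by a factor the documents do not allow me to estimate.

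**The time window.** The parenthesis in 5.5 counts 1 + 6 = 7 days, against 21 in its own sentence. Protocol 5.5.1 and 5.7 collect unsolicited AEs for 21 days or up to Day 21, and SAP 4.2.1 and 4.2.2 analyse them over Day 1 to Day 21. The combined solicited and unsolicited tables over the solicited period (Protocol 6.4.4 and SAP 4.4.1.7) are a 7-day analysis window. They are a separate matter and are not affected.

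**The case against.** The lists are nested. Nothing in 5.5 says that an event meeting only g is non-serious, and 8.1 says plainly that it is serious. Section 8 governs reporting, its opening leads directly into 8.1, and 8.2 asks for seriousness criteria in the eCRF. A site would have to overlook 8.1 to go wrong. Two of the three references in 5.5.2 only close cautions that severe is not the same as serious; the causality reference alone attaches an action.

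The event would not vanish either. Section 5.5.2 requires an outcome for every unsolicited AE and records whether medical attention was received. Section 5.5.3 has the investigator follow participants at later contacts after any AE report. Medically attended events are tabulated with exact intervals (Protocol 6.4.4, SAP 4.4.1.7), and an event needing intervention would normally appear there.

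All of this stands, and it lowers both the likelihood and the cost of an error. It does not remove the contradiction. The opening of Section 8 names neither list, and the part of the protocol on detecting and assessing events cites only the shorter one.

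A reader might infer that the SAE endpoint will be undercounted, or that one misjudged event would turn one SAE among 250 into none. The documents do not support either. The second needs the only SAE in the trial to meet g alone and also to be misclassified. The eCRF and SAE form wording, which may settle what sites do, is not in the documents.

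**Conclusion.** The protocol is internally inconsistent as written: it gives two SAE definitions for a primary endpoint, and 5.5.2 cites the one without the important-medical-event criterion. This should be corrected, though the expected effect is small. It amounts to about 0.014 to 0.086 participants with an event meeting only g, a 1.4% to 8.3% chance of any, before misclassification. Those figures rest on the plan's illustrative rate (1% at 6 months, linear), full enrolment of 250, and my assumed 5% to 30% share. The mismatch in the text is certain; its practical effect is not known.

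The 7-day parenthesis is a secondary slip. A reader might infer that unsolicited AEs are collected for only a week. The collection and endpoint sections cited above say otherwise, and the Day 8 call and Day 22 visit also gather them, so no loss is claimed.

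**What to change.** - Replace the a-to-e list in Protocol 5.5 with a reference to Section 8.1, so that every reference in 5.5.2 leads to the same criteria as the SAP. This also brings in the explanatory notes in 8.1, which 5.5 lacks.
- Check that the seriousness prompts in the eCRF and SAE form match 8.1.
- Do not copy the SAP list into the protocol. Its note under item d (disability) repeats the life-threatening note, where 8.1 has a disability note: "This definition is not intended to include experiences of relatively minor medical significance".
- Reconcile the parenthesis in 5.5 with the 21-day collection and the Day 1 to Day 21 analysis, and check that the diary card does not carry the 7-day wording.

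The cost is a one-line reference, one corrected parenthesis and a form check, by protocol amendment or site memo. No procedures, visits or participants are added.
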